4.4.5. Subgroup Analyses

Subgroup analyses will be conducted to assess the consistency of treatment effect within various subgroups defined by the following baseline characteristics:

- Age (years) [≥ 65 ; < 65]
- Sex [Male; Female]
- Race [White; All other races]
- Region [North America; Western Europe; Rest of World]
 - Region groups may be adjusted if < 20 patients included in any category
- NIS [< 50 ; ≥ 50]
- Previous tetramer stabilizer use [Yes; No]
- Genotype [V30M; non-V30M]

- FAP stage [I; II & III]
- Cardiac Subpopulation [Yes; No]

Subgroup analyses will be performed for the primary endpoint, mNIS+7, and key secondary endpoint, Norfolk QoL-DN, at Month 9 using separate [ANCOVA](#) models with covariate (baseline value) and factors (treatment group; genotype [not applicable to genotype subgroup analyses]), and at Month 18 using an [MMRM](#) with covariate (baseline value), factors (treatment group; visit; genotype [not applicable to genotype subgroup analyses]), and an interaction term (treatment group by visit). A forest plot will be generated to illustrate the estimated treatment effect along with 95% CI within each subgroup.

4.4.6. Component/Domain Analyses

Component analyses will be conducted to assess the consistency of treatment effect on the change from baseline at Month 9 for each component of mNIS+7 (Section [9.1.1](#)) and Norfolk QoL-DN domains (Section [9.1.2](#)). The analyses will be performed at Month 9 using the [ANCOVA/MI](#) model used for the corresponding endpoint, and at Month 18 using the [MMRM](#) used for the corresponding endpoint. A forest plot will be generated to illustrate the estimated treatment effect along with 95% CIs for each component/domain.

4.5. Pharmacodynamic Analyses

The PD parameters include serum TTR and vitamin A. All summary tables and figures will be based on assessments within 21 days after last dose of patisiran or within 84 days after last dose of vutrisiran. Assessments more than 21 days after last dose of patisiran or more than 84 days after last dose of vutrisiran will be presented in listings and individual patient plots only.

Summary tables will be provided for observed values, changes and percentage changes from baseline for each scheduled time point by treatment group for TTR and vitamin A during the study (also see details in Section [6.1](#)).

In addition to TTR percent reduction analyses specified in Section [4.4.3.3](#), the following parameters, derived using all available TTR samples within the specified windows (including nontrough and unscheduled), will be summarized using descriptive statistics:

- Maximum percentage reduction in serum TTR and vitamin A over 9 and 18 months
- Mean percentage reduction in serum TTR and vitamin A over 9 and 18 months
- Mean percentage reduction in serum TTR at steady-state from Month 6 to 9 and from Month 6 to 18

Subgroup analysis for maximum and mean percentage reduction in serum TTR described above will be provided for the following subgroups:

- Age (years) [≥ 65 ; < 65]
- Sex [Male; Female]
- Race [White; All other races]
- Previous tetramer stabilizer use [Yes; No]

- Genotype [V30M; non-V30M]
- Weight (kg) [<65 ; ≥ 65]

Summary of TTR levels over time for patients in the patisiran group before and after the switch to vutrisiran will be presented to evaluate maintenance of serum TTR levels following switch from patisiran to vutrisiran.

All PD data will be displayed in data listings.

4.6. Pharmacokinetic Analyses

4.6.1. Study Variables

4.6.1.1. Concentration Data

For vutrisiran, plasma concentrations of ALN-TTRSC02(siRNA) will be obtained. For patisiran, plasma concentrations of ALN-18328(siRNA), Dlin-MC3-DMA and PEG₂₀₀₀-C-DMG will be obtained. Concentration values that are below the limit of quantification (LLOQ or BLQ) will be set to zero for analysis.

4.6.1.2. Plasma Pharmacokinetic Parameters

Model independent PK parameters to be calculated and summarized descriptively include:

- Study days 1 and 253:
 - Predose levels for vutrisiran and patisiran
 - Observed concentration 3-hour, 6-hour, 24-hour postdose (C_p [3 hr, 6 hr, 24hr]) for vutrisiran and 30-min, 6 hour, 24-hour postdose (C_p [30 min, 6 hr, 24 hr]) for patisiran
 - AUC₀₋₂₄ for vutrisiran
 - Observed trough concentration (C_{trough}) for patisiran
 - Observed maximum concentration (C_{max}) for vutrisiran
 - Time of observed maximum concentration (T_{max}) for vutrisiran
- All other visits:
 - Predose levels for vutrisiran and patisiran
 - Observed concentration 3-hour postdose (C_p [3 hr]) for vutrisiran and patisiran

4.6.2. Statistical Methods

Descriptive statistics for plasma concentration will include the number of patients, mean, SD, coefficient of variation (CV), geometric mean, geometric mean CV, median, minimum, and maximum.

The plasma C_{max} , AUC, C_p (predose, 3 hr, 6hr, 24 hr), and T_{max} of vutrisiran will be summarized by nominal sampling day as well as the plasma C_p (predose, 30 min, 6 hr, 24 hr) and C_{trough} of ALN-18328 (siRNA), Dlin-MC3-DMA and PEG₂₀₀₀-C-DMG for patisiran. In

addition, for vutrisiran only, ratios of Day 253 vs Day 1 AUC and Cmax will be summarized. Mean concentrations (+SD) as well as individual concentrations will be plotted versus nominal sampling time.

Subgroup analysis of vutrisiran plasma Cmax, AUC, Tmax, and ratios of Day 253 vs Day 1 AUC and Cmax will be provided for the following subgroups:

- Age (years) [≥ 65 ; < 65]
- Sex [Male; Female]
- Race [White; All other races]
- Previous tetramer stabilizer use [Yes; No]
- Genotype [V30M; non-V30M]
- Weight (kg) [< 65 ; ≥ 65]

Plasma concentration data will be presented in by-patient listings.

The PK-PD relationship between the plasma concentration and the percent change from baseline in TTR protein and vitamin A will be explored graphically for vutrisiran and ALN-18328 (siRNA) of patisiran separately.

The PK exposure-response relationships for primary endpoint (mNIS+7) and incidence of relevant AEs may also be explored. These may be summarized by exposure quartiles at 9-months for vutrisiran.

Population PK and exposure-response modeling will be reported separately.

4.7. Safety Analyses

Safety analyses will be conducted using the Safety population. All safety summaries will be descriptive and will be presented by treatment group.

4.7.1. Study Drug Exposure

Last exposure date during the 18-month Treatment Period is defined as the earliest of the following dates:

- Last dose date + treatment-specific window (83 days for vutrisiran; 20 days for patisiran)
- Analysis cutoff date
- End of study date
- Week 84 dose date (start of Legacy Treatment Extension Period)
- RTE Day 1 dose date (start of RTE Period)

Duration of drug exposure will be defined as last exposure date – first dose date + 1. Duration of drug exposure, the total number of doses received, and total amount of study drug received will be summarized by descriptive statistics. Summaries of the numbers and percentages of patients

with no missing dose, and the number of missing doses per patient will also be provided. The total volume infused or injected will be summarized as well.

Study drug exposure data collected in the CRFs of study drug administration will also be summarized for each dose or infusion. The numbers and percentages of patients with complete, partial, and missing dose administrations will be summarized. Complete and partial administration is defined as follows:

- Patisiran:
 - Complete: $\geq 80\%$ (≥ 160 mL) of the planned infusion volume (200 mL)
 - Partial: $> 0\%$ to $< 80\%$ (> 0 to < 160 mL) of the planned infusion volume (200 mL)
- Vutrisiran:
 - Complete: 100% administered
 - Partial: $> 0\%$ to $< 100\%$ administered

For the patisiran group, the number of patients who experienced interruptions of infusions for any reason will be tabulated, as well as the number of patients with infusion interruptions due to an infusion-related reaction (IRR).

For the vutrisiran group, the above drug exposure summaries applicable to vutrisiran will also be provided by vial vs prefilled syringe dose presentations. Vutrisiran doses with missing dose presentation information before the date of first prefilled syringe administration to any patient will be treated as vial dose presentations.

Duration of exposure to vial and prefilled syringe dose presentations of vutrisiran will also be summarized.

Dosing information for each patient will be presented in a data listing.

4.7.2. Adverse Events

This Phase 3 study will use the APOLLO study as an external control. Patient-level data from this study will be compared with patient-level data from APOLLO for relevant AE summaries only.

AEs will be coded using the MedDRA coding system (version 23.0 or later) and displayed in tables and data listings using SOC and preferred term.

Analyses of AEs will be performed for those events that are considered treatment-emergent, defined as any AE with onset during or after the administration of study drug through 28 days following the last dose of patisiran or 84 days following the last dose of vutrisiran. In addition, any event that was present at baseline but worsened in intensity or was subsequently considered drug-related by the Investigator through the end of the study will be considered treatment-emergent. Events with a fully or partially missing onset date will be assumed to be treatment emergent unless it can be unequivocally determined (from the partial onset date and/or a partial or complete stop date) that the event occurred prior to the first administration of study drug.

Adverse events will be summarized by the numbers and percentages of patients reporting a given AE. A patient contributes only once to the count for a given AE (overall, by SOC, by preferred term). Overall event counts and event rates may also be summarized.

An overall summary of AEs will include the number and percentage of patients, as well as events and event rates, with any AE, any AE assessed by the Investigator as related to treatment, any severe AE, any severe AE related to treatment, any serious AE (SAE), any SAE related to treatment, any AE leading to treatment discontinuation, any study drug related AE leading to treatment discontinuation, any AE leading to study discontinuation, any study drug related AE leading to study discontinuation, and any deaths.

Tabulations by SOC and preferred term will be produced for the following: all AEs; AEs related to treatment; severe AEs; AEs leading to infusion interruption (patisiran only); AEs leading to drug interruption; AEs leading to treatment discontinuation; AEs leading to stopping study participation; and SAEs. Adverse events and AEs related to treatment will also be tabulated by preferred term. Adverse events and SAEs will also be summarized by SOC and preferred term for the cardiac subpopulation. Subgroup tabulations by SOC and preferred term for AEs and SAEs will be provided for the following subgroups:

- Age (years) [≥ 65 ; < 65]
- Sex [Male; Female]
- Race [White; All other races]
- Region [North America; Western Europe; Rest of World]
 - Region groups may be adjusted if < 20 patients included in any category
- Genotype [V30M; non-V30M]
- FAP stage [I; II & III]
- Weight (kg) [< 65 ; ≥ 65]

Separate tables will present the number and percentage of AEs by maximum relationship to study drug and by maximum severity. Patients who report multiple occurrences of the same AE (preferred term) will be classified according to the most related or most severe occurrence, respectively.

AEs mapping to the standardized MedDRA queries (SMQs) Depression and Suicide/Self-injury, Torsade de pointes/QT prolongation, and Cardiac failure will be summarized by preferred term. Adverse events mapping to the SMQ Drug Related Hepatic Disorder and SMQ Acute Renal Failure will be summarized by SOC and preferred term. Adverse events mapping to Cardiac Arrhythmias high level group term and the SMQ Malignant or Unspecified Tumors will be summarized by high level term and preferred term. Other SMQs or AE groupings may be evaluated.

Separate tables will be provided summarizing signs and symptoms of IRRs (overall and by premedication regimen) and AEs related to premedication by SOC and preferred term for the patisiran group. Injection site reactions will be summarized for the vutrisiran group. Summary table of ISRs by presentation (vial vs prefilled syringe) may be provided. The number and

percentage of patients with AEs, ISRs, and IRRs over time will also be summarized by SOC and preferred term.

All AEs will be presented in patient data listings. Separate listings will be provided for death, SAEs, AEs leading to treatment discontinuation, AEs leading to stopping study participation, and AEs mapping to the SMQ as described above. A listing of ISRs will be provided for the vutrisiran group. Listing of IRRs and AEs related to premedications will also be provided for patisiran group. A listing of patients who underwent liver transplant will also be provided.

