3.2. General Methods

All data listings that contain an evaluation date will contain a study day relative to the day of the first dose of study drug, which is designated as Day 1. On-treatment study days will be calculated as evaluation date – first dose date +1 and pretreatment days will be calculated as evaluation date – first dose date. There is no Day 0.

Categorical descriptives will include the count and percentage of patients (or events, if applicable) within each category (with a category for missing data) of the parameter. Continuous descriptives will include the number of patients, mean, median, standard deviation (SD), standard error (SE), minimum, and maximum values.

Laboratory data (including vitamin A) collected and recorded as below the limit of detection will be set equal to the lower limit of detection for the calculation of summary statistics.

For assessments that are repeated multiple times for the study visit, the average will be calculated unless otherwise noted.

All summaries will be presented by treatment group. Unless otherwise specified, treatment groups in the treatment period will be presented using the following labels:

- Placebo (APOLLO)
 - Presented primarily for efficacy (except TTR) analyses and most AE and baseline summaries
- Vutrisiran (HELIOS-A)
- Patisiran (HELIOS-A)
- Total (HELIOS-A)
 - Presented primarily for patient disposition, protocol deviations, and baseline summaries

In addition, for TTR sensitivity analyses, the following treatment groups will be presented:

- Patisiran (HELIOS-A + APOLLO)
- Patisiran (APOLLO)

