3.2. General Methods

All data listings that contain an evaluation date will contain a study day relative to the day of the first dose of study drug, which is designated as Day 1. On-treatment study days will be calculated as evaluation date – first dose date +1 and pretreatment days will be calculated as evaluation date – first dose date. There is no Day 0.

Categorical descriptives will include the count and percentage of patients (or events, if applicable) within each category (with a category for missing data) of the parameter. Continuous descriptives will include the number of patients, mean, median, standard deviation (SD), standard error (SE), minimum, and maximum values.

Laboratory data (including vitamin A) collected and recorded as below the limit of detection will be set equal to the lower limit of detection for the calculation of summary statistics.

For assessments that are repeated multiple times for the study visit, the average will be calculated unless otherwise noted.

All summaries will be presented by treatment group. Unless otherwise specified, treatment groups in the Treatment Period will be presented using the following labels:

- Placebo (APOLLO)
 - Presented primarily for efficacy (except TTR) analyses and most safety and baseline summaries
- Vutrisiran (HELIOS-A)
- Patisiran (HELIOS-A)
- Total (HELIOS-A)
 - Presented primarily for patient disposition, protocol deviations, and baseline summaries

In addition, for TTR sensitivity analyses, the following treatment groups will be presented:

- Patisiran (HELIOS-A + APOLLO)
- Patisiran (APOLLO)

For analyses on the All Vutrisiran-Treated Population, the following treatment arms will be presented:

- Vutrisiran/Vutrisiran
- Patisiran/Vutrisiran
- Total

These 3 treatment arms represent the respective Vutrisiran (HELIOS-A), Patisiran (HELIOS-A), and Total (HELIOS-A) treatment groups, reflecting the transition from the initial randomized treatment (either vutrisiran or patisiran) during the Treatment Period to vutrisiran in the subsequent Legacy Treatment Extension or RTE periods. The experience while receiving vutrisiran will be summarized.

For analyses on the Re-randomized Population, the following treatment groups will be presented:

- Vutrisiran 25 mg q3M
- [REDACTED]
- Total

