3.9. Planned Analyses

As this study will be ongoing at the time of the primary analysis at Month 9 and the additional analysis at Month 18, the study database will undergo an interim database lock at the Month 9 and Month 18 data cutoff dates (ie, data in EDC will be cleaned, frozen and electronically signed by investigators; external laboratory data will be cleaned and will undergo quality assurance). Additional details regarding the interim database locks will be documented in the study Data Management Plan.

The Month 9 and Month 18 analyses and associated clinical study reports (CSRs) will include all data on or before the respective data cutoff date. For assessments with start and end dates (eg, AEs, medications, medical history), data records with start dates after the specified data cutoff date will be excluded.

[REDACTED]

After the study is completed (ie, all patients discontinue or complete the RTE Period and/or required follow-up visits), the database will undergo a final database lock, and the data will be summarized in a final CSR.

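### At the Month 9 analysis, SOC/preferred-term AE tables with the APOLLO placebo column show crude patient percentages that are not on the same time base (minor)

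*SAP*

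**What the plan says.** Section numbers are those of Amendment 3.

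- **Measure.** Section 4.7.2: "Adverse events will be summarized by the numbers and percentages of patients reporting a given AE", with each patient counted once per event.
- **Rates.** Events and event rates are required in the overall AE summary (any AE, severe AE, SAE, discontinuations, deaths). Beyond that, Section 4.7.2 says only "Overall event counts and event rates may also be summarized".
- **Detailed tables.** Section 4.7.2: "Tabulations by SOC and preferred term will be produced for the following: all AEs", then severe AEs, SAEs and others. No rate is specified for these tables.
- **Over time.** Section 4.7.2 also plans a table of the number and "percentage of patients with AEs, ISRs, and IRRs over time will also be summarized by SOC and preferred term". It defines no intervals and does not list the treatment groups.
- **Placebo column.** Section 4.7.2 compares patient-level AE data with APOLLO for relevant AE summaries. Section 3.2 describes the APOLLO placebo group as "Presented primarily for efficacy (except TTR) analyses and most safety and baseline summaries". Amendment 2 worded it as "Presented primarily for efficacy (except TTR) analyses and most AE and baseline summaries".
- **Data included.** Section 3.9: the Month 9 and Month 18 analyses "will include all data on or before the respective data cutoff date".
- **APOLLO follow-up.** Section 9.1.5 uses a Week 78 placebo assessment as Month 18. No section cuts APOLLO AE data at an earlier time.
- **Treatment-emergent window.** Section 4.7.2 runs it "through 28 days following the last dose of patisiran or 84 days following the last dose of vutrisiran". It names none for placebo.
- **Status.** Section 4.7 makes all safety summaries descriptive.

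**The concern.** A crude percentage rises with time observed. Two crude percentages can be read against each other only if the groups were watched for about the same time, or if the difference in time is shown.

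At the Month 9 analysis nothing in the SAP secures that. A HELIOS-A patient contributes from first dose to the calendar cutoff, so follow-up depends on enrolment date. An APOLLO placebo patient contributes everything collected, up to about Week 78.

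Comparison across the studies is the stated reason for the column: the Amendment 1 history (Section 10.1) says that placebo was added to help compare AE safety with APOLLO. Someone who looks up one preferred term in the Month 9 report would see two percentages side by side and could not tell a difference in risk from a difference in time. The rates in the overall summary do not help at that level.

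**Working it through.** **The plan's own figure.** The SAP gives no number on this point. Its only safety figure (Section 1.4: more than 100 vutrisiran patients, no event, one-year incidence no greater than 3%) reproduces: 1 − 0.05^(1/100) = 2.95%. That statement ties incidence to a fixed period. The AE tables do not.

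**Assumptions, none of them stated in the current SAP.** The hazard is constant, and each group's mean follow-up t stands for all its patients.

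- Vutrisiran: uniform enrolment over E months, cutoff at the last patient's Month 9 visit, no dropout. Mean follow-up is 9 + E/2, so E = 6 gives 12 months and E = 9 gives 13.5. The cutoff rule comes from Amendment 1, Section 4.4. Amendment 2 moved cutoff details to the Data Management Plan, so it serves here only to set a range.
- Placebo: 12 to 14 months. This is below 18 because Section 3.5.1 says that some placebo patients stopped study drug.

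**Formulas.** The crude percentage is 1 − exp(−h·t). Equal percentages in both columns hide a true rate ratio (vutrisiran/placebo) of t_placebo / t_vutrisiran. With no true difference and p affected on placebo, vutrisiran shows 1 − (1 − p)^(t_vutrisiran / t_placebo).

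| Vutrisiran (months) | Placebo (months) | Hidden rate ratio | Vutrisiran % if placebo 20% | Vutrisiran % if placebo 5% |
|---|---|---|---|---|
| 12 | 14 | 14/12 = 1.17 | 17.4 | 4.3 |
| 13.5 | 14 | 14/13.5 = 1.04 | 19.4 | 4.8 |
| 12 | 12 | 12/12 = 1.00 | 20.0 | 5.0 |
| 13.5 | 12 | 12/13.5 = 0.89 | 22.2 | 5.6 |

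**Outside this range, both ways.**

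- Fewer placebo patients leave: a constant discontinuation rate reaching 30% by Month 18 gives a mean of 15.1 months. Against 12 months on vutrisiran the hidden ratio is 15.1/12 = 1.26.
- Later cutoff: Section 3.7 lets a COVID-delayed Month 9 assessment run to Study Month 15. If the last patient used all of that delay and E = 6, mean vutrisiran follow-up could approach 15 + 6/2 = 18 months. The hidden ratio would fall to 14/18 = 0.78 or 12/18 = 0.67, so the direction reverses.

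**Why a rate alone is not enough.** Suppose that 20% of each group has a first event spread evenly over months 0 to 3, and none later. Patient-years per patient, ending at the first event, are (0.2 × 1.5 + 0.8 × t)/12.

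- t = 12: 9.9/12 = 0.825, so 20/0.825 = 24.2 per 100 patient-years.
- t = 14: 11.5/12 = 0.958, so 20/0.958 = 20.9 per 100 patient-years.

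The ratio is 1.16 with identical risk, while the first-9-month percentage is 20% in both groups.

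**The case against.** The strongest reply is that this argues from silence. Section 1 says that table specifications are documented separately, and Section 4.7.2 limits APOLLO to relevant summaries. Columns and cut points may be settled elsewhere. That stands as a limit on scope: the point covers only tables that carry the placebo column. It does not remove the point, because the measure and the data-inclusion rule are set in the SAP, and the SAP itself chooses which summary must have rates.

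The reply also notes that Section 3.2 cuts both ways. If its general rule puts placebo in the main tables, it may put placebo in the over-time table too, and that table could then give a time-aligned reading by preferred term. This stands in part. The intervals are undefined, so the reading is possible but not assured.

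It adds that the top-line categories have rates, that Section 4.7.2 permits more, that nothing inferential depends on these tables, and that Amendment 3 mainly serves the extension and Month 18. All of that stands and keeps the point small. Section 3.9 still covers the Month 9 analysis, and Amendment 2 has the same measure and cutoff rule.

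A reader might infer that placebo percentages will be nearly doubled in favour of vutrisiran. At 9 versus 18 months the hidden ratio is 18/9 = 2.00, and an event seen in 10% at 9 months would show 19.0% on placebo. The documents do not support that reading. It needs every vutrisiran patient to stop at 9 months and every placebo patient to be followed for 18. A calendar cutoff gives earlier enrollees more than 9 months, and some placebo patients stopped study drug.

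**Conclusion.** The point holds as a minor one. Followed as written, the Month 9 SOC/preferred-term tables of AEs, severe AEs and SAEs that carry the APOLLO placebo column show crude percentages over unmatched observation times.

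Size and direction are unknown. The main scenarios give hidden rate ratios of 0.89 to 1.17, a range that includes 1.00, and other assumptions move it either way. All of this rests on assumed mean follow-up and a constant hazard, so it illustrates the problem and does not estimate a bias.

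Two stronger inferences should be avoided. The text does not show that the comparison favours vutrisiran, nor that any test or success criterion is affected. The absence of a placebo treatment-emergent window is, taken alone, only an unstated detail.

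**What to change.** In Section 4.7.2, for the SOC/preferred-term tables of AEs, severe AEs and SAEs that carry the placebo column in the Month 9 report:

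1. Add the percentage of patients with onset in the first 9 months from first dose, in both studies. Alternatively, require the planned over-time table to include APOLLO placebo with a 0 to 9 month interval.
2. Add, as a supplement read beside it, an exposure-adjusted incidence rate: patients with the event per 100 patient-years, with time at risk ending at the first event or at the end of the treatment-emergent window. This requires naming the window used for placebo.
3. Keep the crude percentages.

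The cost is SAP wording and extra columns in a few tables. Patient-level APOLLO data are already in use, so nothing new is collected. The downsides are longer tables, later events left out of the 9-month column, early discontinuation that still differs between studies, and a rate that assumes a roughly constant hazard.

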4.9.3. Impact on Adverse Events

An overall summary of AEs mapping to a COVID-19 custom query will include the number and percentage of patients, as well as events and event rates, with any AE, any severe AE, any SAE, any AE leading to treatment discontinuation, any AE leading to study discontinuation, and any deaths. AEs mapping to the COVID-19 custom query will be summarized by high level term and preferred term. Due to the evolving nature of COVID-19-related MedDRA terminology, the COVID-19 custom query will be based on the latest information available at the specified analysis timepoint.

An overall summary of AEs by pandemic phase will include the number and percentage of patients, as well as events and event rates, with any AE, any AE assessed by the Investigator as related to treatment, any severe AE, any severe AE related to treatment, any SAE, any SAE related to treatment, any AE leading to treatment discontinuation, any study drug related AE leading to treatment discontinuation, any AE leading to study discontinuation, any study drug related AE leading to study discontinuation, and any deaths. AEs and SAEs will be summarized by pandemic phase, SOC, and preferred term. The number and percentage of patients with AEs during the pandemic will also be summarized over time by SOC and preferred term.

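### Reaction tables by vial v prefilled syringe, and SOC/PT adverse event tables by pandemic phase, default to patient percentages that vary with exposure, not only with risk

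*SAP*

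**What the plan says.** All references are to SAP Amendment 3.

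- **Default measure.** Section 4.7.2: "Adverse events will be summarized by the numbers and percentages of patients reporting a given AE". Each patient counts once per event term. Rates are optional: "Overall event counts and event rates may also be summarized".
- **ISRs by presentation.** Section 4.7.2: "Summary table of ISRs by presentation (vial vs prefilled syringe) may be provided". Nothing is said about the measure, about the denominator (all vutrisiran patients, or only those given that presentation), or about how a reaction is assigned to a presentation.
- **Order of introduction.** Section 4.7.1: "Vutrisiran doses with missing dose presentation information before the date of first prefilled syringe administration to any patient will be treated as vial dose presentations". Vial use therefore came first.
- **Exposure by presentation.** Section 4.7.1: "the above drug exposure summaries applicable to vutrisiran will also be provided by vial vs prefilled syringe dose presentations". Those summaries include the number of doses, and duration of exposure to each presentation is also planned. Neither is tied to the ISR table as a denominator.
- **All vutrisiran treatment.** Section 6.2 repeats the ISR summaries of Section 4.7.2 over every period on vutrisiran. Patients first randomized to patisiran enter only from the extension.
- **Pandemic phase.** Section 4.9.3 gives events and event rates for the overall adverse event summary by phase. For the detailed tables it says only: "AEs and SAEs will be summarized by pandemic phase, SOC, and preferred term". Section 4.9.4 plans treatment duration by phase.
- **Status.** Section 4.7 makes all safety summaries descriptive.

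**The concern.** The share of patients with at least one event rises with the number of injections, or the time, over which they are observed. That is harmless when the columns have similar exposure. Here they need not.

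The vial was used before the syringe, so a patient who began on vial gives early doses to one column and later doses to the other, in numbers that may differ. A patient who stopped before the syringe arrived contributes to vial only. Pandemic phases are calendar periods. One of the candidate definitions in Section 4.9.2, given there for efficacy, has a middle phase running from March to June 2020, at most four months. For a patient treated for 18 months across all three phases, at least 14 months fall in the other two, so at least one of those lasts 7 months or more.

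The Amendment 1 history gives regulatory assessment of the syringe as the reason for splitting by presentation. A percentage that moves with the dose split could make either presentation look better tolerated, or hide a real difference. A phase table could likewise suggest a pandemic effect that is only phase length.

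**Working it through.** The SAP states no figure on this point, so there is none to reproduce. The check shows how the default measure behaves when the true risk is the same in both columns.

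**Inputs**
- From the SAP: vutrisiran every 3 months (Section 1.1), with planned doses up to and including Week 72 (Section 2, Month 18 Efficacy PP Population). That is Weeks 0, 12, 24, 36, 48, 60 and 72, or 7 doses.
- Assumed: the same ISR risk *p* per injection for vial and syringe, independent between injections. The splits of the 7 doses are also assumed, because the SAP gives none.

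**Step 1. Patient percentage.** With *k* doses, the share of patients with at least one ISR is 1 − (1 − p)^k. At p = 1%:

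| Vial + syringe doses | Vial | Syringe | Syringe/vial |
|---|---|---|---|
| 6 + 1 | 5.85% | 1.00% | 0.17 |
| 5 + 2 | 4.90% | 1.99% | 0.41 |
| 4 + 3 | 3.94% | 2.97% | 0.75 |
| 3 + 4 | 2.97% | 3.94% | 1.33 |
| 2 + 5 | 1.99% | 4.90% | 2.46 |

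For 5 + 2, vial is 1 − 0.99^5 = 4.90% and syringe is 1 − 0.99^2 = 1.99%. With p from 0.5% to 5%, the 5 + 2 ratio stays between 0.40 and 0.43 and the 3 + 4 ratio between 1.30 and 1.33. The result depends on the split far more than on the assumed risk.

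**Step 2. Denominator.** If half the patients had switched and the syringe column were divided by all vutrisiran patients, its 5 + 2 figure would fall from 1.99% to 0.5 × 1.99% = 1.00%. The unstated denominator matters as well.

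**Step 3. Events per injection.** For 5 + 2 the expected rates are (5 × 1%)/5 = 1% for vial and (2 × 1%)/2 = 1% for syringe. The ratio is 1.00 for every split.

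**Step 4. What a per-injection rate leaves behind.** Suppose the first dose carries 3% and later doses 1%, whatever the presentation (assumed). For 5 + 2, the patient percentages are 1 − 0.97 × 0.99^4 = 6.8% v 2.0%. The per-injection rates are (3% + 4 × 1%)/5 = 1.4% v 1.0%. The gap shrinks but does not close, because the vial column still holds the first dose.

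**Step 5. Pandemic phase.** Assume a constant 0.3 first events per patient-year, with 7 months before and 11 months during the pandemic.
- Patient percentages: 1 − exp(−0.3 × 7/12) = 16.1% and 1 − exp(−0.3 × 11/12) = 24.0%.
- As a rate, both phases show 30 per 100 patient-years.

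**The case against.** The strongest reply is that the plan does not commit to a wrong table. The ISR table by presentation only may be produced, its measure is not written down, Section 4.7.2 allows event rates, and table specifications are kept in a separate document (Section 1). Per-patient counting is an inference from the default. This stands, and it limits the point to what happens if the default is applied.

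A reader might go further and infer that the syringe must show fewer reactions because it arrived later and so covers fewer doses. The SAP does not support that. It establishes the order of introduction but gives no dose counts by presentation. The direction reverses once the syringe covers more doses than the vial. That could happen in the summaries under Section 6.2, which add extension doses and patients switched from patisiran.

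The other side can also say that much of the context is already planned: doses and duration by presentation, a listing of ISRs, ISRs over time, event rates in the overall summary by phase, and treatment duration by phase. Within a phase, vutrisiran and patisiran come from the same randomization, so phase length does not systematically favour either arm. All of this is fair. It means a careful reader could work out crude overall rates from other outputs. It does not give a rate for each SOC and preferred term by phase, or say which presentation a reaction belongs to.

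Finally, no test or success criterion uses these tables. That is correct and sets the weight of the point.

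**Conclusion.** The point holds as a minor one. Under the stated default, the optional ISR table by presentation and the planned SOC/PT tables by pandemic phase would compare columns with possibly unequal exposure, and could show differences where risk is equal. At 1% per injection the illustration gives 4.9% v 2.0% for 5 vial and 2 syringe doses, and 3.0% v 3.9% for 3 and 4. For phases of 7 and 11 months it gives 16% v 24%.

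The risks, dose splits, event rate and phase lengths are all assumptions, so these figures show how large the artefact can be, not how large it will be or which way it will go. The documents do not support saying that the syringe is favoured by construction, or that the plan has fixed a per-patient count for the ISR table.

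**What to change.** - **Section 4.7.2.** State that, if the ISR table by presentation is produced, it reports ISR events per injection given, with the numbers of injections and of patients exposed to each presentation. Attribute each ISR to the presentation of the most recent dose. Apply the same rule to the repeat under Section 6.2.
- **Time on drug.** Where numbers allow, show the rates descriptively by dose number, or separately for Vutrisiran/Vutrisiran and Patisiran/Vutrisiran, since a per-injection rate alone does not remove this confounding (Step 4). This is an optional refinement; small cells will limit it.
- **Section 4.9.3.** Add exposure-adjusted event rates (per 100 patient-years) to the SOC/PT tables by phase, using the treatment duration by phase already planned in Section 4.9.4.

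The cost is a few sentences in the SAP and a small amount of programming, mainly linking each ISR to the preceding dose. Dose counts by presentation and duration by phase are already planned, and no new data are needed.
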